The sole objective in this study is to evaluate if routine amounts of opioids given for tonsillectomy in children have greater amounts of respiratory depression in children with documented obstructive sleep apnea when compared with patients that do not have obstructive sleep apnea

Section E: Protocol Risks/Subjects

E1. Risk Category

Category 3: Research involving greater than minimal risk and no prospect of direct benefit to the individual subject, but likely to yield generalizable knowledge about the subject's disorder or condition.

E2. Subjects

Gender:

Both

Age:

Child (3-12 yrs), Infant/Toddler (0-36 mos)

Ethnicity:

All Ethnicities

Primary Language:

English, Spanish

Groups to be recruited will include:

Asymptomatic patients with chronic conditions, healthy; Patients

Which if any of the following vulnerable populations will be recruited as subjects?

Children

Vulnerable populations require special protections. How will you obtain informed consent, protect subject confidentiality, and prevent undue coercion?

Parents will be approached as ask to participate in the study. They will be informed that this is completely voluntary and that they can choose to avoid participation and/or revoke their participation at any point. Their participation or lack thereof will not change or alter the care their child will receive. The risks include loss to confidentiality and we will reduce this risk by only having the PI and co-investigators collect data which will be stored only on the BCM firewall. Additionally, there is a risk of apnea with all opioids however this risk is routinely managed by pediatric anesthesiologists and encountered in nearly all anesthetics.

E3. Pregnant woman/fetus

Will pregnant women and/or fetuses (as described in 45 CFR 46 Subpart B) be enrolled in the research?

No

E4. Neonates

Will neonates of uncertain viability or nonviable neonates (as described in 45 CFR 46 Subpart B) be enrolled in the research?

No

E5. Children

Will children be enrolled in the research?

Yes

Section F: Design/Procedure

F1. Design

Select one category that most adequately describes your research:

c) Pilot

Discuss the research design including but not limited to such issues as: probability of group assignment, potential for subject to be randomized to placebo group, use of control subjects, etc.

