The Principal and/or co-investigators will identify children meeting enrollment criteria from the daily operative list at Texas Children's Hospital main campus. Those meeting enrollment criteria will be approached by the PI and/or co-investigators.

The study is a prospective randomized trial to identify the effect of opioids on children with obstructive sleep apnea

F2. Procedure

Patient Identification The Principal and/or co-investigators will identify children meeting enrollment criteria from the daily operative list at Texas Children's Hospital main campus. Those meeting enrollment criteria will be approached by the PI and/or co-investigators.

Control Group: Patients undergoing tonsillectomy/adenotonsillectomy without tonsillectomy Children presenting for tonsillectomy/adenotonsillectomy for recurrent infection. Children with negative sleep studies will be included. Those without formal sleep studies will be screened using the OSA 18 questionnaire, a validated clinical assessment score for pediatric sleep-disordered breathing.

Those with negative questionnaire scores will be included.

Study Group: Patients with Moderate to Severe OSA as documented by formal polysomnography For the study group, patients will be included if they have undergone formal sleep study evaluations. Stratification will be based on the polysomnography testing using the apnea hypopnea index (AHI) and/or the number desaturation events according to the McGill Scoring system for pediatric OSA. Patients with AHI greater than 6 will be considered to have moderate to severe OSA and thus eligible for inclusion

All patients will undergo general anesthesia per the usual practice at Texas Childrens Hospital according to the preferences of the anesthesiology attending physician. Induction will be sevoflurane/+nitrous oxide followed by intravenous access secured.

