Endotracheal intubation using a RAE endotracheal tube will be performed with the size selected using the formula: Predicted Size Cuffed Tube = (Age / 4) + 3. Following endotracheal intubation, spontaneous ventilation will be maintained without the use of continuous positive pressure. Sevoflurane will be reduced to maintain between 0.5-0.7 MAC according to the Drager Apollo anesthesia machine. The patient will be allowed to establish their respiratory equilibrium for 3 minutes following intubation on 0.21% oxygen. Baseline tidal volume (TV), respiratory rate (RR) and end-tidal carbon dioxide (ETCO2) will be recorded. fentanyl 1mcg/kg will be administered as a bolus (usual clinical practice). The TV, RR, ETCO2 will be recorded, at 5 and 10 minutes After opioid administration. Apnea or desaturation (<92%) will be treated by assisting ventilation as required (standard practice). After 10 minutes,(to a repeated dose effect) a second dose of 1mcg/kg will be administered with the same TV, RR, ETCO2 recorded for 5 minutes.

Surgery will commence as usual with additional medication to be administered at the discretion of the anesthesiology providers. No change to standard practice will occur the research portion will be prospectively recorded the TV, RR, ETCO2 following opioid administration to calculate change from baseline (pre-opioid), routine fentanyl administration for these procedures is 2 mcg/kg

Section G: Sample Size/Data Analysis

G1. Sample Size

How many subjects (or specimens, or charts) will be used in this study?

Local: 50 Worldwide: 50

Please indicate why you chose the sample size proposed:

Our sample size is based on a recent 2019 landmark paper investigating a similar question in adults with obstructive sleep apnea we propose to enroll 20 control patients and 30 patients with documented obstructive sleep apnea

G2. Data Analysis

Provide a description of your plan for data analysis. State the types of comparisons you plan (e.g. comparison of means, comparison of proportions, regressions, analysis of variance). Which is the PRIMARY comparison/analysis? How will the analyses proposed relate to the primary purposes of your study?

The primary outcome will be measurement of continuous variables of tidal volume, respiratory rate and end tidal CO2. these will be reported as means with SD, regression analysis will be performed for patients falling into the moderate and severe categories of obstructive sleep apnea by sleep study.

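### The tidal volume comparison has no stated scale and no adjustment for body size in children aged 0 to 12 years; the primary analysis should adjust for baseline tidal volume and weight

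*Combined protocol and SAP*

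**What the plan says.** G2 (Data Analysis) defines the primary outcome: "The primary outcome will be measurement of continuous variables of tidal volume, respiratory rate and end tidal CO2". Of these three variables it says that "these will be reported as means with SD". The only model it names concerns OSA severity: "regression analysis will be performed for patients falling into the moderate and severe categories". No covariate is listed for that model.

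F2 (Procedure) says the recordings will be used "to calculate change from baseline (pre-opioid"), without saying whether the change is absolute, per kg or relative. The only stratification in F2 is by polysomnography.

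Section D gives the sole objective as the amount of opioid respiratory depression in children with OSA "when compared with patients that do not have obstructive sleep apnea". E2 ticks the age categories "Child (3-12 yrs), Infant/Toddler (0-36 mos"). F2 forms the groups by diagnosis. Controls are "Children presenting for tonsillectomy/adenotonsillectomy for recurrent infection", with a negative sleep study or questionnaire. The other group is "Study Group: Patients with Moderate to Severe OSA as documented by formal polysomnography". G1 plans 20 controls and 30 children with OSA.

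**The concern.** Tidal volume in mL grows with the child. Subtracting the child's own baseline does not necessarily remove size: if two children lose the same share of their baseline, the bigger one loses more mL. Where the fall scales with size, the spread of body size in a 0 to 12 year sample adds to the SD of mL change and makes the OSA v control comparison less precise, even when the groups are of equal average size. If the groups differ in size, part of any TV difference between them reflects size rather than OSA, and it can create or hide an effect.

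F1 calls the study randomized, but that gives no protection here, because OSA status is not assigned. Nothing in the design balances age or weight between the groups. The comparison at stake is the study's only objective, in 50 children. RR and ETCO2 are not affected by this point.

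**Working it through.** **The plan's own figure.** The sample of 50 cannot be reproduced, because G1 gives no significance level, power, effect size or SD. The figures below are therefore illustrations.

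**Inputs from the documents.** 20 control and 30 OSA children; change from pre-opioid baseline; no covariates.

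**Assumed inputs.** Control mean weight 20 kg, lognormal, CV 35% or 50%. True baseline TV = weight × 5 mL/kg (SD 0 or 1). Mean fall 30%, or 30% v 40% when there is an OSA effect, with SD 10 or 20 points. Noise of 0 or 15% on each reading. The same mL/kg at baseline in both groups. Welch test at two-sided 5%, which the plan does not name.

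**Step 1: arithmetic that needs no test.** mL fall = share × 5 mL/kg × weight.
- The same 30% fall: 0.30 × 5 × 20 = 30 mL; × 22 kg = 33 mL; × 25 kg = 37.5 mL.
- A true 30% v 40% difference at 20 kg: 0.10 × 5 × 20 = 10 mL.
- A 10% weight difference alone therefore gives 3/10 = 30% of that signal, and a 25% difference gives 7.5/10 = 75%.

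**Step 2: three models of the fall.** (A) a share of the child's own baseline; (B) a fixed mL/kg; (C) the same mL in every child whatever the size (30 v 40 mL when there is an effect). A and B scale with size; C does not. Each was simulated over all combinations of the settings above. Ranges are minimum to maximum.

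**Step 3: false positives with no OSA effect, nominal 5%.**

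| Analysis of TV change | A, B: OSA group 10% heavier | A, B: 25% heavier | C: 25% heavier |
|---|---|---|---|
| mL, unadjusted | about 6-12% | about 10-36% | about 5% |
| Percent | about 5% | about 5% | about 10-30% |
| mL/kg | about 5% | about 5% | about 10-30% |
| mL on group + baseline TV + weight | about 3-6% | about 3-6% | about 3-6% |

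With equal average weights, every analysis stays near 5%.

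**Step 4: power at equal average weights.**

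| Analysis of TV change | A, B (30% v 40%) | C (30 v 40 mL) |
|---|---|---|
| mL, unadjusted | 17-59% | about 20-93% |
| Percent | 25-93% | about 19-58% |
| mL/kg | about 21-93% | about 18-60% |
| Adjusted model | 21-90% | at most about 1 point below mL |

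Under A and B, unadjusted mL has 21-79% of the efficiency of percent change, so 50 children count as about 50 × 0.207 = 10 to 50 × 0.790 = 40. Within the same setting, the adjusted model gains about 4 to 48 power points over unadjusted mL.

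**Step 5: cross-check with other inputs.** At 6 mL/kg (SD 1.2), falls of 30% v 45% with SD 15 points and weight CV 40%, power is 60% on mL change, 86% on mL/kg and 93% on percent. With no effect and the OSA group 20% lighter (weight CV 30-40%), mL change rejects 18-21% of the time. The distortion therefore does not depend on which group is larger.

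**The case against.** The strongest reply is that the harm rests on several conditions. The documents do not say that mL is intended. If the change in F2 means percent change and the fall scales with size, the problem described for mL largely disappears and a line of clarification would do. This stands, and it is why the point is conditional. It does not make percent or mL/kg safe by default: under model C those scales lose power and produce the false positives. Model C may be the least plausible of the three, but the documents do not settle the matter.

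Second, apart from the group sizes every number is assumed, and the ranges are wide. E2 gives eligible age categories, not the ages that will be enrolled, and the groups may turn out similar in size. This also stands: the figures show direction and plausible range, not the expected error of this study.

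Third, F1 classes the study as a pilot, and G2 names no OSA v control test at all. The error rates therefore describe a test that the plan does not contain, and the missing primary comparison is a wider gap that this change alone does not close. That is fair. But section D makes the group comparison the only objective, so whatever comparison is written into G2 will need a way of handling size.

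**Conclusion.** The point holds in conditional form. As written, the plan is a size-unadjusted comparison of TV on an unstated scale, between groups formed by diagnosis, over an eligible range of 0 to 12 years. If change is in mL and the fall scales with size, precision is lost. If the groups also differ in size, the comparison is confounded. If percent or mL/kg was meant, that harm goes, but the same kind of error appears should the fall not scale with size. Only the adjusted model kept its error rate under all three models of the fall, with no material loss of power in any. That result assumes a similar baseline TV per kg in the two groups, and it was tested with weight, not age, as the size covariate.

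A reader might infer three stronger things that the documents do not support:
- that the trial's TV result is confounded: no passage reports that the groups differ in size or that mL will be used;
- that mL change always costs precision: under model C it is as powerful as the adjusted model or nearly so, and often far more powerful than percent or mL/kg;
- that switching to percent or mL/kg is enough: it is enough only if the fall scales with size.

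This should be changed, because the repair is nearly free, but it is not on its own a reason to doubt the study.

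**What to change.** In G2, state that the primary TV analysis of OSA v control is a regression of TV change from pre-opioid baseline (in mL) on group, with baseline TV and weight as covariates; age is a possible substitute for weight. Report percent change or mL/kg change, on a stated weight, as a secondary descriptive scale. Nothing needs to change for RR or ETCO2 on this account.

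The cost is two or three sentences, one or two degrees of freedom and slightly more analysis work. No new measurement is needed: F2 already records baseline TV, the per-kg dose requires weight, and the tube-size formula requires age. With noisy readings and widely varying falls, the gain over unadjusted mL may be only a few power points.

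### G2 does not say how the three or more post-fentanyl readings per child will be analysed, and its one named model leaves out the OSA-versus-control comparison

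*Combined protocol and SAP*

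**What the plan says.** F2 (Procedure) sets the measurement schedule. Before any opioid, "Baseline tidal volume (TV), respiratory rate (RR) and end-tidal carbon dioxide (ETCO2) will be recorded". After the first fentanyl bolus, "The TV, RR, ETCO2 will be recorded, at 5 and 10 minutes After opioid administration". After that, "a second dose of 1mcg/kg will be administered with the same TV, RR, ETCO2 recorded for 5 minutes". Each child therefore gives one baseline and at least three post-opioid values of each variable. The second-dose wording could mean one reading or several. F2 closes by saying that the readings serve to compute change from the pre-opioid value.

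G2 (Data Analysis) makes the three variables the primary outcome and says that "these will be reported as means with SD". Its only model is in the clause "regression analysis will be performed for patients falling into the moderate and severe categories of obstructive sleep apnea by sleep study". It gives no response variable, time point, per-child summary, covariates, error structure or significance level.

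Section D states a single objective: children with OSA compared with children without it. On numbers, G1 says "we propose to enroll 20 control patients and 30 patients with documented obstructive sleep apnea".

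**The concern.** OSA status and severity vary between children, while the readings repeat within a child. Readings from the same child are correlated, so the analysis must either reduce them to one value per child or model the correlation. G2 commits to neither.

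Three consequences follow.

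- If an analyst entered every reading as a separate row of an ordinary regression, each child would count three or more times. Standard errors would be too small, and a difference in opioid response would be declared too often.
- If an analyst picked one time, the test would be valid but would set aside information already collected from a small sample. The choice of time could also be made after seeing the data.
- The regression is confined to children with moderate or severe OSA. Adding a within-child term to it would still leave the study's objective without a model.

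**Working it through.** **Inputs from the documents.** 20 control and 30 OSA children (G1); one baseline and readings at 5 and 10 minutes after dose 1 (F2); at least one reading after dose 2 (F2). So m = 3 post-opioid readings at minimum.

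**Assumed, because the documents give no figure.** Two-sided 5% test; within-child correlation ρ = 0.5 (range 0.3 to 0.8); equal variance at each time; a group difference of 0.8 SD for power; a 15 v 15 split of moderate and severe OSA where that contrast is simulated.

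**The plan's own figure.** The only design figure is the total of 50. It cannot be reproduced, because G1 cites an adult paper and gives no effect size, SD, alpha or power. By the normal approximation, 20 v 30 with one value per child detects, with 80% power, (1.960 + 0.842) × √(1/20 + 1/30) = 2.802 × 0.2887 = 0.81 SD.

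**Why 0.5 is a reasonable centre.** F2 uses change from one shared baseline. With unit variances and a common raw correlation r, two changes have covariance 1 − r and variance 2(1 − r) each. Their correlation is (1 − r)/[2(1 − r)] = 0.5 whatever r is.

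**False-positive rate if rows were pooled.** The true variance of the group contrast exceeds the pooled-row variance by the factor 1 + (m − 1)ρ. The rate is 2[1 − Φ(1.96/√(1 + (m − 1)ρ))].

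| m = 3 | factor | formula | simulated 20 v 30 | simulated 15 v 15 |
|---|---|---|---|---|
| ρ = 0.3 | 1.6 | 12.1% | 11.7% | 12.0% |
| ρ = 0.5 | 2.0 | 16.6% | 16.7% | 16.9% |
| ρ = 0.8 | 2.6 | 22.4% | 22.3% | 22.9% |

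The simulations used 20,000 trials per setting. With one mean per child, simulated rates were 4.7% to 5.2%. If the second-dose period gave five one-minute readings (m = 7), the formula gives 24%, 33% and 42% at ρ = 0.3, 0.5 and 0.8.

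**Power for OSA versus control, one time against all three.** The SD of a child's three-reading mean is √((1 + 2ρ)/3), in units of the single-reading SD. For a constant 0.8 SD difference at 20 v 30, by the noncentral t distribution:

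| ρ | SD of mean | one time | mean of three |
|---|---|---|---|
| 0.3 | 0.730 | 77.5% | 96.1% |
| 0.5 | 0.816 | 77.5% | 91.4% |
| 0.8 | 0.931 | 77.5% | 83.1% |
| 0.9 | 0.966 | 77.5% | 80.3% |

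The normal approximation gives 79.1% and 92.4% at ρ = 0.5, so the gain is 13 to 14 points there. By the t calculation it falls to about 3 points at ρ = 0.9.

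**The case against.** The strongest reply is that G2 is silent rather than wrong. A mixed model is a regression, as is a regression with one row per child. F2's use of change from baseline points towards a per-child quantity. The study is classed as a pilot in F1, no alpha or test is stated anywhere, and the primary outcome is to be reported descriptively.

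Most of this stands. A reader might infer that G2 prescribes an ordinary regression on pooled rows, so that the trial's error rate is 17%. The documents do not support that. They never say that rows are pooled, and they state no 5% level to be inflated. The 17% is an illustration of one route left open.

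The power argument is also conditional. A single-time analysis is legitimate, and the gain assumes a similar difference at every time. F2 gives a second dose specifically to look at repeated dosing, so the difference may change between doses.

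What does not stand is that change from baseline settles the matter. Each child has at least three changes, and neither F2 nor G2 says which one, or what combination, is analysed. Unadjusted testing at all three times would give an any-of-three error of about 8% to 13% (simulated, ρ from 0.9 to 0.3). Pilot status does not remove the need to specify a regression that the plan intends to run, and nothing elsewhere supplies a model for OSA versus control.

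**Conclusion.** The point holds as under-specification. F2 creates repeated measures; G2 does not name the child as the unit, does not use the readings together, and gives no model for the sole objective.

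The error-rate figure, about 17% (12% to 23%), applies only if rows are pooled, and rests on a two-sided 5% test, three readings and ρ from 0.3 to 0.8. It would be higher if the second-dose period yields several readings. The precision figure, 77.5% against 91.4% (96.1% to 83.1%), rests on a constant 0.8 SD difference at 20 v 30 and shrinks as correlation rises or if the effect differs between doses. That the plan is silent is certain from the text; the size of the consequence is not. The change is inexpensive and worth making.

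**What to change.** Amend G2 as follows.

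- State that the child, not the reading, is the unit of analysis, and state the significance level.
- For each of TV, RR and ETCO2, fit one repeated-measures model to both groups, using all post-fentanyl readings. Make OSA versus control the main contrast and moderate versus severe a secondary one.
- Include group, time, group-by-time and the pre-opioid baseline as fixed effects, with a random intercept per child or a within-child covariance, and small-sample degrees of freedom (for example Kenward-Roger).
- Report the contrast averaged over the post-opioid times and at each time, and so by dose, with 95% confidence intervals.
- State how many readings the second-dose period will yield.
- Flag readings taken during assisted ventilation, which F2 allows for, and report the analysis with and without them.

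A simpler alternative is one mean post-opioid value per child, regressed on group and baseline with one row per child. It is not identical to the model. Baseline should be a covariate in either version: F1 calls the study randomised, but F2 forms the groups by diagnosis. Baselines may therefore differ, and an unadjusted mean change can then give a different answer.

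The cost is wording and a standard model run, with no extra children or measurements. Intervals will be wider than a pooled-row regression would show, and the averaged contrast gains power only if the group difference is similar across times. That is why the by-time contrasts are kept.
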